6. STUDY ASSESSMENTS

6.1. General Assessments

Study visits for all patients will occur for screening, at baseline, and subsequently for the injections and for the metabolic and immunologic monitoring (see Appendix A). General assessments include:

- Medical history and routine or directed Physical examination
- Concomitant medications
- Adverse events

6.2. Laboratory Assessments

The following laboratory assessments will be performed during the study:

- Chemistry (sodium, potassium, chloride, CO2, glucose, BUN, creatinine)
- Liver function tests (ALT, AST, alkaline phosphatase, total protein, albumin, total and direct bilirubin)
- Hematology (complete blood count with differential and platelets)
- Urine pregnancy test as appropriate
- Islet Autoantibodies
- Viral serology: antibodies to HIV, hepatitis B (antiHBcAb, HbsAg,), hepatitis C (HCV),Cytomegalovirus (CMV IgG)) Epstein-Barr Virus (EBV IgG and IgM). Viral load will be determined if indicated.
- PPD
- Samples for titers from routine childhood immunizations.

6.3. Mechanistic Outcome Assessments

TrialNet will perform immune and genetic assays to further understand mechanisms that may be underlying the Type 1 disease process and response to therapy. For this purpose, samples for PBMC, DNA, RNA, plasma, and serum will be obtained. HLA testing will be done.

The primary mechanistic studies are those which measure GAD65-specific immune responses. The principle objective is to identify measures of immunity to GAD which distinguish between subjects receiving two or three injections of GAD in alum, as compared to those receiving alum injections alone.

Additional objectives are:

(i) To determine whether these measures of GAD immunity reflect immune deviation, changes in GAD epitope recognition or amplification of GAD regulatory function;

(ii) To evaluate other T1D-associated immune responses, such as anti-proinsulin or anti-IA2, as markers for antigen-spreading and bystander effects; and

(iii) To correlate changes in GAD65-specific immune responses with levels of c-peptide over the 24-month duration of the trial.

6.4. Metabolic Outcome Assessments

Metabolic assessments will consist of:

- Glucose records and reports of hypoglycemia including those that are symptomatic and confirmed with capillary glucose measurement, symptomatic and unconfirmed, and major hypoglycemia
- Insulin dose
- HbA1c
- Mixed meal tolerance test (MMTT)
- •

6.5. Neurologic Assessments

The patients will undergo a standardized clinical neurological examination. The neurological tests are performed in order to detect possible mild signs of neuromuscular disease such as disturbance of strength, balance and coordination. The neurological examination includes:

- Extremity reflexes
- Romberg (balance and coordination)
- Walk on a line, 2 meters (balance and coordination)
- Standing on one leg, left and right, 15 seconds per leg (balance and coordination)
- Finger-finger (coordination)
- Finger-nose (coordination)
- Mimic (cranial nerves)
- Babinski reflex (central function)
- Muscle strength (shake hands) biceps, triceps, distal extensors and flexors.

6.6. Visit Windows

The screening MMTT must occur at least 21 days after the day of diagnosis. Randomization must occur within 100 days from the date of diagnosis and the first injection should be administered within 37 days of the MMTT. The subsequent treatment visits should be no longer than +7 days from the target date. Immunization earlier than the target date is limited to -2 days. The target window for each subsequent injection will be based on the actual date the previous injection was given. There is a +/-3 day window around the target dates for the visit after the first injection and a +3 day window around the target dates for the visits immediately after the 2nd and 3rd injections. The window for all subsequent visits is +/- 2 weeks.

Patients who receive at least one injection will be considered active participants. If patients are febrile when scheduled for injection, treatment will be postponed until the patient is afebrile.

7. PARTICIPANT SAFETY

7.1. Expected Side Effects and Adverse Events

7.1.1. Influenza-like Symptoms

In previous studies, the majority of Adverse Events were due to mild influenza-like symptoms, with nasopharyngitis the most common Adverse Event. However, no significant differences were seen between the treatment groups.

7.1.2. Injection Site Reactions

In previous studies, injection site reactions occurred in a limited number of patient visits. All reactions were mild and most (in particular, "tenderness") occurred primarily on the day of the "prime" injection and "boost" injection four weeks later. No significant differences were seen between the treatment groups.

7.2. Other safety issues

7.2.1. Pregnancy

Pregnant and lactating women will not be included in the study. Females must have a negative pregnancy test prior to enrolling in the study and will be required to use birth control during the study. At every study visit the sexual activity of female participants of reproductive age will be re-assessed. If a subject who was previously sexually inactive becomes sexually active, she will be counseled about the need to use a reliable form of birth control. Female subjects will also be required to undergo urine pregnancy tests at regular intervals and prior to each dosing. Subjects will be requested to avoid pregnancy for 2 years.

8. ADVERSE EVENT REPORTING AND SAFETY MONITORING

8.1. Adverse Event Definition

8.1.1. Adverse Event

In this clinical trial, an adverse event is any occurrence or worsening of an undesirable or unintended sign, symptom or disease whether or not associated with the treatment and study procedures.

Throughout the study, the investigator must record all adverse events on source documentation, and those that are Grade 2 or greater must be recorded on the appropriate adverse event form as described below. The investigator should treat participants with adverse events appropriately and observe them at suitable intervals until the events resolve or stabilize.

Adverse events may be discovered through:

- observation of the participant;
- questioning the participant;
- unsolicited complaint by the participant.

In questioning the participant the questioning should be conducted in an objective manner.

8.1.2. Serious Adverse Event

For this trial, an adverse event associated with the treatment or study procedures that suggests a significant hazard, contraindication, side effect or precaution (as described below) is to be reported as a serious adverse event (SAE). A serious adverse event (experience) or reaction is any untoward medical occurrence that:

- results in death,
- is life-threatening,
- requires inpatient hospitalization or prolongation of existing hospitalization,
- results in persistent or significant disability/incapacity, or
- is a congenital anomaly/birth defect.

Important medical events that may not result in death, be life threatening, or require hospitalization may be considered serious adverse events when, based upon appropriate medical judgment, they may jeopardize the patient and/or may require medical or surgical intervention to prevent one of the outcomes listed above.

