8.2. Adverse Event Reporting and Monitoring

Study personnel will assess adverse events and the use of concomitant medications throughout the study. All adverse events will be recorded on source documents and those \geq grade 2 will be reported to the TrialNet Coordinating Center as described below. They will be graded as to severity according to common toxicity criteria or study-specific criteria and the investigator will make a determination as to the relation to therapy. Events will be assessed and reported in accordance with the ICH Guideline for Good Clinical Practice and per the guidance of the DHHS Office for Human Research Protections (OHRP). An adverse event report must be completed for all adverse events (AE) of Grade 2 or greater severity regardless of relationship to therapy. For reporting serious adverse events (SAE), the TrialNet MedWatch Form should also be completed and faxed to the TNCC within 24 hours of when the site was notified of the event. This will be reviewed by the TrialNet Medical Monitor, the TrialNet Safety Committee, and the DSMB as appropriate. Deaths must be reported immediately. Event outcome and other follow-up information regarding the treatment and resolution of the event will be obtained and reported when available, if not known at the time the event is reported. The followup information should contain sufficient detail to allow for a complete medical assessment of the case and an independent determination of possible causality.

Adverse events will be assessed by the TrialNet Medical Monitor. The DSMB will conduct regular safety reviews approximately every three to six months (and, as needed) of adverse events by treatment group assignment. Serious adverse events as well as adverse events leading to study discontinuation will be reviewed by the DSMB.

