8.3. Protecting Against or Minimizing Potential Treatment Risks

Subjects will not be enrolled who have other active serious medical problems. Frequent monitoring of patients with history, physical examination, and laboratory studies will allow for early identification of adverse events. Subjects with pre-existing neurologic disease will be excluded from the study, and a structured neurologic exam will be performed at study visits. Every attempt will be made to minimize the number of venipunctures.

All dosing will take place in a facility that has resuscitation capabilities, and subjects will be closely monitored during and after the injection.

Subjects will be counseled about the need to report any change in health status between

or at the time of visits.

Subjects will be counseled by study personnel and requested to avoid pregnancy for 2 years

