11.1.5. Data and Safety Monitoring Board (DSMB)

The DSMB will meet approximately every 6 months to review efficacy issues and adverse events prepared by the Coordinating Center. All adverse events will be recorded on the adverse event forms, which will be sent to the local IRBs, per their reporting requirements, and to the Coordinating Center. The DSMB will independently evaluate whether the adverse events constitute grounds to discontinue the study.

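### Section 8.1.2 contradicts itself on whether a serious adverse event must be associated with treatment, and Sections 8.1.1 and 8.2 contradict 11.1.5 on whether Grade 1 events go on the forms

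*Protocol*

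**What the plan says.** **SAE definition.** Protocol Section 8.1.2 opens with a reporting instruction. The event to be reported as an SAE is "an adverse event associated with the treatment or study procedures that suggests a significant hazard, contraindication, side effect or precaution", with a pointer to the description that follows. That description begins "A serious adverse event (experience) or reaction is any untoward medical occurrence that" and lists the outcomes: death, threat to life, hospitalization, disability and birth defect. It does not mention association with treatment.

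**Adverse event definition.** Section 8.1.1 is explicitly free of causality: "any occurrence or worsening of an undesirable or unintended sign, symptom or disease whether or not associated with the treatment and study procedures".

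**What goes on a form.** Section 8.1.1 has every event noted in source documents, but only "those that are Grade 2 or greater must be recorded on the appropriate adverse event form". Section 8.2 agrees, requiring a report for "all adverse events (AE) of Grade 2 or greater severity regardless of relationship to therapy". Section 11.1.5 says otherwise: "All adverse events will be recorded on the adverse event forms", and these forms go to the local review boards and the Coordinating Center.

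**Routes.** Under Section 8.2 an SAE additionally needs a MedWatch form within 24 hours of the site's learning of it, and SAEs are reviewed by the DSMB. Adverse events in general are reviewed by the DSMB by treatment group about every three to six months.

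**Neurologic examination.** Section 6.5 says it is done "in order to detect possible mild signs of neuromuscular disease". Section 8.3 says "a structured neurologic exam will be performed at study visits".

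**The concern.** The two sentences of Section 8.1.2 give different answers for a hospitalization that the investigator thinks has nothing to do with the injections. By the first it is not to be reported as an SAE; by the second it is an SAE. The first is the one phrased as an instruction to report, so a site could reasonably act on it. Because the trial is masked, the site would make that causality judgement without knowing whether the patient received GAD-alum or alum alone.

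What is at stake is speed and classification. Only SAEs carry the 24-hour deadline and the explicit case review. This matters more because Section 4.3 opens enrollment to younger children after safety reviews that are each triggered by 20 actively treated subjects.

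The second conflict concerns completeness. Section 9.2 makes the count and severity of adverse events a secondary outcome. If some sites submit Grade 1 events and others do not, that outcome mixes two collection rules. It also leaves unclear whether a mild neurologic sign, the kind of finding the examination is meant to pick up, leaves the source documents as an adverse event.

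**Working it through.** No power or sample-size figure is at issue. The check is a comparison of the rules, followed by a rough size.

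**1. Serious event judged unrelated to treatment and procedures, Grade 2 or greater**

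| Step | 8.1.2, first sentence | 8.1.2, second sentence |
|---|---|---|
| SAE? | No | Yes |
| MedWatch form within 24 hours (8.2) | Not triggered | Required |
| Adverse event report to the Coordinating Center (8.2) | Required | Required |
| Periodic DSMB review by arm (8.2) | Yes | Yes |
| DSMB review as an SAE (8.2) | Not triggered | Yes |

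The two readings differ in the second and last routes only. Deaths are to be reported immediately under Section 8.2 on either reading.

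**2. Grade 1 event, not serious**

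| Step | 8.1.1 and 8.2 | 11.1.5 |
|---|---|---|
| Source documents | Yes | Yes |
| Adverse event form to the Coordinating Center | No | Yes |

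The two rules cannot both hold.

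**3. How often the causality condition could matter**

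Inputs, from Section 3.2.1:
- Newly diagnosed type 1 diabetes trial: 12 SAEs over 30 months in 70 patients, none considered treatment-related.
- Phase IIa LADA trial follow-up: 11 SAEs, none considered treatment-related.

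Total: 12 + 11 = 23 SAEs, of which 0 were considered treatment-related. The protocol does not report whether any was associated with a study procedure.

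**4. Illustrative number in this trial**

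Assumptions: all 70 earlier patients were followed for the full 30 months, the same SAE rate applies here, and all 126 patients are followed for 2 years.

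- Earlier follow-up: 70 × 2.5 = 175 patient-years.
- Rate: 12 / 175 = 0.069 per patient-year.
- Follow-up here: 126 × 2 = 252 patient-years.
- Expected SAEs: 252 × 12 / 175 = 17.3.
- Exact Poisson 95% limits for a count of 12: χ²(0.025; 24 df)/2 = 6.20 and χ²(0.975; 26 df)/2 = 20.96. Multiplied by 252/175 = 1.44, these give 8.9 and 30.2.

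So about 17 SAEs, with a range of about 9 to 30. The 12 earlier events occurred in nine patients (four placebo, five treated). Some patients had more than one event, so the Poisson interval is probably somewhat too narrow.

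**The case against.** **The SAE sentence can be read benignly.** It points forward to the description below it, that description has no causality condition, and Section 8.2 requires reporting in line with ICH GCP. A careful site might well report every serious event. This stands in part: the protocol does not settle on a relatedness-only SAE, and the defect is a contradiction. It still needs resolving, because the restrictive sentence is the one worded as an instruction.

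**A reader might infer that unrelated serious events never reach the DSMB.** The protocol does not support that. Section 8.2 collects Grade 2 or greater events whatever the causality judgement and has them reviewed by arm.

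**A reader might infer that none of the 23 earlier SAEs would have counted under the first sentence.** That goes too far. The sentence also covers association with study procedures, on which the protocol gives no information for those events.

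**A reader might infer that mild neurologic signs are wrongly kept off the SAE route.** A sign that meets no listed outcome is not an SAE on either reading. Its only possible gap is the adverse event form. Even that is not certain: the examination is a standardized assessment in its own right, Section 11.1.3 has sites forward their data collection forms, and Section 6.5 does not equate a mild sign with Grade 1. However, the protocol names no route by which these findings reach the DSMB.

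**A Grade 2 threshold is a legitimate choice.** This stands. Limiting forms to Grade 2 or greater is defensible, and mild injection-site reactions give no separate reason to change it: Section 7.1.2 reports no significant group difference and no grading scale for them. The fault is that Section 11.1.5 states a different rule.

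**A reader might infer bias between arms.** Randomization is stratified by site and sites are masked, so differing site practice should fall about equally on the arms. The harm is to completeness and absolute rates.

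**The absence of a neurologic row in Appendix 1 adds little.** The table does not list every assessment (insulin dose has no row either), and the examination may be part of the physical examination.

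**Conclusion.** The point holds as two contradictions in the safety reporting rules.

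First, Section 8.1.2 gives two incompatible tests for an SAE. For a serious event judged unrelated, what can be lost is the 24-hour report and the SAE classification. Collection and periodic by-arm review remain, provided the event is Grade 2 or greater. Since none of 23 earlier SAEs was considered treatment-related, the ambiguity could affect most of the SAEs in this trial, which would number about 17 (range about 9 to 30) at the earlier type 1 diabetes trial's rate. That figure assumes an unchanged rate and full follow-up, and it indicates scale only.

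Second, Sections 8.1.1 and 8.2 disagree with Section 11.1.5 on Grade 1 events. Capture of those events, possibly including mild neurologic signs, and the adverse event secondary outcome depend on which section a site follows. The protocol does not allow the number of affected Grade 1 events to be estimated.

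The first contradiction is the more important, because it bears on prompt reporting in a trial that enrolls children.

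**What to change.** 1. In Section 8.1.2, remove the condition of association with treatment or procedures and the hazard qualifier attached to it. Define an SAE by the listed outcomes, together with the existing provision for important medical events, and state that causality plays no part. The investigator's judgement of relatedness is still recorded under Section 8.2.
2. State one grade threshold for the adverse event form and use it in Sections 8.1.1, 8.2 and 11.1.5. Either rule can work if it is the same throughout; if Grade 2 is kept, describe the secondary outcome in Section 9.2 as covering Grade 2 or greater.
3. Whichever threshold is chosen, have abnormal findings on the neurologic examination, of any grade, sent to the Coordinating Center and tabulated by arm for the DSMB.

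The cost is a wording amendment, a few more SAE forms, and some Grade 1 entries. Sample size, visits and the primary analysis do not change.

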8.1.3. Unexpected Adverse Event

An adverse event is considered unexpected when the nature (specificity) or severity of the event is not consistent with the risks described in the protocol or informed consent document for a particular protocol required intervention.

8.1.4. Grading Event Severity

TrialNet has adopted usage of the National Cancer Institute (NCI) Common Technology Criteria for Adverse Events (CTCAE) with the exception of hypoglycemia and hyperglycemia for classification to describe the severity of adverse events. For this study, a reportable hypoglycemic event is defined as those resulting in loss of consciousness, seizure, or requiring assistance of others due to altered state of consciousness. A hyperglycemic event is one resulting in DKA.

8.2. Adverse Event Reporting and Monitoring

Study personnel will assess adverse events and the use of concomitant medications throughout the study. All adverse events will be recorded on source documents and those \geq grade 2 will be reported to the TrialNet Coordinating Center as described below. They will be graded as to severity according to common toxicity criteria or study-specific criteria and the investigator will make a determination as to the relation to therapy. Events will be assessed and reported in accordance with the ICH Guideline for Good Clinical Practice and per the guidance of the DHHS Office for Human Research Protections (OHRP). An adverse event report must be completed for all adverse events (AE) of Grade 2 or greater severity regardless of relationship to therapy. For reporting serious adverse events (SAE), the TrialNet MedWatch Form should also be completed and faxed to the TNCC within 24 hours of when the site was notified of the event. This will be reviewed by the TrialNet Medical Monitor, the TrialNet Safety Committee, and the DSMB as appropriate. Deaths must be reported immediately. Event outcome and other follow-up information regarding the treatment and resolution of the event will be obtained and reported when available, if not known at the time the event is reported. The followup information should contain sufficient detail to allow for a complete medical assessment of the case and an independent determination of possible causality.

Adverse events will be assessed by the TrialNet Medical Monitor. The DSMB will conduct regular safety reviews approximately every three to six months (and, as needed) of adverse events by treatment group assignment. Serious adverse events as well as adverse events leading to study discontinuation will be reviewed by the DSMB.

8.3. Protecting Against or Minimizing Potential Treatment Risks

Subjects will not be enrolled who have other active serious medical problems. Frequent monitoring of patients with history, physical examination, and laboratory studies will allow for early identification of adverse events. Subjects with pre-existing neurologic disease will be excluded from the study, and a structured neurologic exam will be performed at study visits. Every attempt will be made to minimize the number of venipunctures.

All dosing will take place in a facility that has resuscitation capabilities, and subjects will be closely monitored during and after the injection.

Subjects will be counseled about the need to report any change in health status between

or at the time of visits.

Subjects will be counseled by study personnel and requested to avoid pregnancy for 2 years

9. STATISTICAL CONSIDERATIONS AND ANALYSIS PLAN

Analyses of study data will be conducted to address all objectives of the trial and other interrelationships among data elements of interest to the investigators and of relevance to the objectives of the study. Analyses by gender and race/ethnicity, as appropriate, are also planned.

Primary analysis of treatment effect will be conducted under the intention-to-treat principle of eligible patients whereby outcome data from all eligible patients will be included regardless of treatment compliance.

